#### **Summary tables will be presented as follows:**

##### **1. Adverse Event Overview**

The number and percentage of subjects experiencing treatment-emergent adverse events will be summarized for the following adverse event categories.

- Any AE
- Any AE that was assessed as related to study drug by the investigator
- Any severe AE
- Any serious AE (SAE)
- Any SAE that was assessed as related to study drug by the investigator

- Any AE leading to discontinuation of study drug.
- Any AE leading to death.
- Any deaths
- Areas of Safety Interest

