**Diagnosis and Main Criteria for Inclusion/Exclusion (Continued):****Main Exclusion (Continued):**

- Severe gastro-intestinal disease, such as a known active gastro-duodenal ulcer,
- Inability to understand the complexity of FUMADERM® dosing regimen,
- Any other exclusionary condition provided in Fumaderm® local label,
- Any of the following risk factors for renal toxicity:
  - peripheral vascular disease
  - diabetes mellitus with microalbuminuria (UACR > 30 mg/g), at Screening Visit,
  - systolic blood pressure measurement of > 140 mmHg or a diastolic blood pressure measurement of > 90 mmHg at the Screening visit, unless there is confirmation from an internist or a cardiologist that no renal or cardiovascular risk is associated with the elevated blood pressure.
  - history of congestive heart failure (NYHA Class III or IV\*)

**Investigational Product:** Risankizumab**Doses:** 150 mg at Weeks 0 and 4, and 16.**Mode of Administration:** Subcutaneous Injection (SC) (pre-filled syringe)**Investigational Product:** FUMADERM® INITIAL and FUMADERM® provided as study medication**Doses:** QD to TID**Mode of Administration:** Oral**Duration of Treatment:** The treatment duration will be 16 weeks for risankizumab and 24 weeks for FUMADERM®.**Criteria for Evaluation:****Efficacy:**

The primary efficacy endpoint is the proportion of subjects with a  $\geq 90\%$  improvement in Psoriasis Area and Severity Index (PASI90) at Week 24.

Secondary efficacy variables are:

PASI, Body Surface Area (BSA), static Physician Global Assessment (sPGA), Palmoplantar psoriasis Severity Index (PPASI), Psoriasis Scalp Severity Index (PSSI), Nail Assessment in Psoriasis and Psoriatic Arthritis (NAPPA-CLIN), Total Score Psoriasis Symptom Scale (PSS), Dermatology Life Quality Index (DLQI), Short Form 36 (SF-36) Physical Component Summary (PCS) and Mental Component Summary (MCS) Scores, Patient Benefit Index (PBI), Hospital Anxiety and Depression Scale (HADS) Patient Global Assessment (PtGA), European quality of life – 5 dimensions 5 Level (EQ-5D-5L)

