**5.5.2.2****Identity of FUMADERM® INITIAL and FUMADERM® Investigational Product**

The two formulations of Fumaderm are used in this study are FUMADERM® INITIAL and FUMADERM® gastro-resistant tablets, FUMADERM® INITIAL being the low dose formulation to be taken in the first weeks of treatment before moving to FUMADERM®.

**Table 5. FUMADERM® INITIAL and FUMADERM® Pre-Specified Dosing Schedule (in the Absence of an Adjustment to the Efficacy and/or Safety Response):**

Week	Dosage (n of Tablets/Day)		
	Morning	Noon	Evening
FUMADERM® INITIAL			
0	-	-	1
1	1	-	1
2	1	1	1
FUMADERM®			
3	-	-	1
4	1	-	1
5	1	1	1
6	1	1	2
7	2	1	2
8 – 24*	2	2	2

\* Last intake of FUMADERM® in the morning on the day of Week 24 visit.

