**6.1.1 Definitions****6.1.1.1 Adverse Event**

An adverse event (AE) is defined as any untoward medical occurrence in a patient or clinical investigation subject administered a pharmaceutical product and which does not necessarily have a causal relationship with this treatment. An adverse event can therefore be any unfavorable and unintended sign (including an abnormal laboratory finding), symptom, or disease temporally associated with the use of a medicinal (investigational) product, whether or not the event is considered causally related to the use of the product.

Such an event can result from use of the drug as stipulated in the protocol or labeling, as well as from accidental or intentional overdose, drug abuse, or drug withdrawal. Any worsening of a pre-existing condition or illness is considered an adverse event.

Worsening in severity of a reported adverse event should be reported as a new adverse event. Laboratory abnormalities and changes in vital signs are considered to be adverse events only if they result in discontinuation from the study, necessitate therapeutic medical intervention, and/or if the investigator considers them to be adverse events.

An elective surgery/procedure scheduled to occur during a study will not be considered an adverse event if the surgery/procedure is being performed for a pre-existing condition and the surgery/procedure has been pre-planned prior to study entry. However, if the pre-existing condition deteriorates unexpectedly during the study (e.g., surgery performed earlier than planned), then the deterioration of the condition for which the elective surgery/procedure is being done will be considered an adverse event.

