- b. Subjects that discontinue the study prior to the end of the study will have a follow-up phone call within 15 weeks after the last dose of FUMADERM® provided as study medication for collection of safety data. Subjects that elect to enroll into a separate extension study will not require the Week 31 Follow-Up phone call as part of this trial.
- c. Update history.
- d. Serum pregnancy test in all women at screening and if the urine pregnancy test is positive at any other visit. Urine pregnancy tests are to be performed in all women of child bearing potential prior to administration of study drug at all dosing visits.
- e. Height and weight will be measured at the Screening Visit only (with shoes off).
- f. Targeted laboratory samples should be limited to CBC with differential count (hematology), serum creatinine (substrates) and ALT, AST, gamma-GT and AP (enzymes).
- g. (FSH) To be done at Screening in all women aged ≤ 55 years with no menses for 12 or more months without an alternative medical cause.
- h. Infection screening consists of Hepatitis B Surface Antigen (qualitative), Hepatitis B Surface Antibody (qualitative), Total Hepatitis B Core Antibodies (qualitative), Hepatitis B Virus DNA (quantitative) reflex, Hepatitis C Virus RNA (quantitative) reflex, HIV-1 and HIV-2 Antibody (qualitative), PPD/QuantiFERON-TB.
- i. For FUMADERM® INITIAL and FUMADERM® provided as study medication only.
- j. Prior to other procedures.
- k. SC risankizumab 150 mg at Week 0/Day 1, Week 4 and Week 16. Risankizumab will be administered at the study site by authorized site personnel (e.g., study nurse) after all study procedures have been completed.
- l. Oral FUMADERM® daily starting at Week 0/Day 1 and until Week 24 (the last dose will be in the morning of the day of Week 24 visit). FUMADERM® INITIAL starting at Week 0/Day 1 until Week 2 and FUMADERM® starting at Week 3, both at starting dose of 1 tablet per day, followed by a dose increase of one tablet per week, depending on efficacy response and tolerability. The maximum dose of FUMADERM® of 6 tablets per day should not be exceeded.
- m. PK and ADA samples are collected only from the subjects receiving risankizumab.

---

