**11.0 Safety Analysis****11.1 General Considerations**

Safety evaluations include AE monitoring, physical examinations, vital sign measurements, and clinical laboratory testing (hematology, chemistry, and urinalysis) as a measure of safety and tolerability for the entire study duration. Safety summaries will be provided using the safety population as defined in Section 5.1. Pairwise comparisons of risankizumab vs FUMADERM® will be performed in the Safety Population. AEs will be analyzed using Fisher's exact test, only P values  $\leq 0.100$ , when rounded to three digits, will be presented.

Missing safety evaluations will not be imputed.

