## **11.2 Analysis of Adverse Events**

### **11.2.1 Treatment-Emergent Adverse Events**

Treatment-emergent adverse events (TEAE) are defined as events with an onset date on or after the first dose of study drug until 15 weeks (105 days) following the last dose of risankizumab or 1 week (7 days) after the last dose of FUMADERM® or until rollover into the extension study. In a sensitivity analysis, adverse events with an onset date until 7 weeks (49 days) after the last dose of FUMADERM® or until rollover into the extension study will be included. In this sensitivity analysis, the observation period for TEAEs will be identical for both treatment arms, i.e., up to the 31 week safety follow-up call.

SAEs and protocol-related non-serious AEs with onset after informed consent but before the first study drug administration will be considered as pretreatment events and reported separately. Posttreatment events for FUMADERM® are included in the above sensitivity analysis.

If an incomplete onset date is collected for an adverse event, the event will be assumed to be treatment-emergent unless there is other evidence that confirms that the event is not treatment-emergent (e.g., the event end date is prior to the study drug start date).

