**Pre-treatment SAEs will be summarized as follows:**

- A by-subject listing will be provided

**Treatment-emergent adverse events leading to death or premature discontinuation of study drug will be summarized as follows:**

- Grouped by SOC and PT
- Separate listings by subject for deaths and premature terminations of study drug due to adverse events will be provided.

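### The count of AEs leading to discontinuation of study drug compares the arms over unequal opportunity (112 versus 168 days), and the SAP has no rule for AE-driven study withdrawal after the last risankizumab injection

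*SAP*

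**What the plan says.** **Dosing.** The protocol synopsis says: "The treatment duration will be 16 weeks for risankizumab and 24 weeks for FUMADERM". Footnote k of the Study Activities table (protocol Appendix C) gives "SC risankizumab 150 mg at Week 0/Day 1, Week 4 and Week 16". The footnote to protocol Table 5 gives "Last intake of FUMADERM® in the morning on the day of Week 24 visit".

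**The row.** Item 1 of SAP 11.2.1 (Adverse Event Overview) lists nine categories, one of which is "Any AE leading to discontinuation of study drug". The same section plans a table by system organ class and preferred term: "Treatment-emergent adverse events leading to death or premature discontinuation of study drug will be summarized as follows".

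**The comparison.** SAP 11.1 states: "Pairwise comparisons of risankizumab vs FUMADERM® will be performed in the Safety Population". It names Fisher's exact test for AEs.

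**Which AEs are eligible.** An AE is treatment-emergent from first dose "until 15 weeks (105 days) following the last dose of risankizumab or 1 week (7 days) after the last dose of FUMADERM", or until rollover. A sensitivity analysis extends the FUMADERM limit to 49 days.

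**Stopping drug and leaving the study are different things in the SAP.** SAP 8.0 counts them on separate lines. The compliance text in SAP 9.0 refers to subjects who stopped study drug but remained in the study. The safety tables use only the drug version.

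**The concern.** The category needs a drug that can still be discontinued. On FUMADERM that condition holds up to the Week 24 visit. On risankizumab, going by the schedule, it holds only up to the third injection. Take two subjects who each leave the study at Week 18 because of the same AE. The FUMADERM subject is plainly counted. The risankizumab subject has already received every planned dose, and no rule says whether the case counts. Sites could record it differently.

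Fisher's test on proportions of subjects makes no allowance for this. If such cases are not counted, part of any difference between the arms comes from the dosing schedule and not from tolerability. The study objective includes comparing safety, and protocol 3.0 cites discontinuation due to adverse events in 24% of FUMADERM subjects in an earlier controlled trial. The row is therefore likely to be read closely.

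**Working it through.** **1. Reproduce the stated durations.** Appendix C puts Week 0, Week 16 and Week 24 at Days 1, 113 and 169.
- Risankizumab: 113 − 1 = 112 days = 16 weeks.
- FUMADERM: 169 − 1 = 168 days = 24 weeks.

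Both match the synopsis. The ratio of opportunity is 168/112 = 1.5.

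**2. Set this against the treatment-emergent window, for a subject who completes dosing.**
- Risankizumab: 113 + 105 = Day 218.
- FUMADERM, main analysis: 169 + 7 = Day 176.
- FUMADERM, sensitivity analysis: 169 + 49 = Day 218.

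A risankizumab AE with onset from Day 114 to Day 218 is treatment-emergent (before any rollover), yet no scheduled dose remains to be stopped.

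**3. Check whether another planned analysis corrects the row.**
- The sensitivity analysis equalises the AE onset window. It does not change how long a dose remains to be stopped.
- Rates per 100 patient-years are planned for any TEAE, serious AEs and areas of safety interest, not for this category.
- SAP 8.0 summarises premature discontinuation with reasons by arm. It does so in the ITT population, without system organ class or preferred term and without a stated test.

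**4. Size on risankizumab.** The documents give no risankizumab rate for this event, so a Week 16 rate q is assumed. With a constant hazard, the rate over a 24-week opportunity is 1 − (1 − q)^1.5. The shortfall is that value minus q, and the number of subjects is 55 times the shortfall.

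| Assumed rate by Week 16 | Rate by Week 24 | Shortfall (points) | Subjects of 55 |
|---|---|---|---|
| 1% | 1.5% | 0.5 | 0.3 |
| 2% | 3.0% | 1.0 | 0.5 |
| 3% | 4.5% | 1.5 | 0.8 |
| 5% | 7.4% | 2.4 | 1.3 |
| 10% | 14.6% | 4.6 | 2.5 |

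**5. Would the conclusion move?** The protocol gives no time point for the 24% FUMADERM figure. Week 16 is assumed, as for the efficacy results of the same trial.
- By Week 16: 0.24 × 55 = 13.2, about 13 subjects.
- By Week 24 under a constant hazard: 1 − 0.76^1.5 = 33.7%, and 0.337 × 55 = 18.6, about 19 subjects.

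| Risankizumab count of 55 | Versus 13 (common Week 16 cut) | Versus 19 (as planned) |
|---|---|---|
| 1 | p = 0.001 | p < 0.001 |
| 2 | p = 0.004 | p < 0.001 |
| 3 | p = 0.013 | p < 0.001 |
| 5 | p = 0.069 | p = 0.002 |

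The cut-off changes the reading at 5 of 55 (9.1%) on risankizumab, and not at 1 to 3 of 55.

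**The case against.** The strongest reply is that nothing is miscounted. Fewer dosing occasions are a feature of the regimen, and the row correctly reports how often each drug was stopped as scheduled. The disposition table will show AE-driven withdrawal after Week 16 if AE is among the recorded reasons, and protocol 5.4.1 applies one common list of withdrawal reasons to both arms. The treatment-emergent window is longer on risankizumab in the main analysis, so the safety plan does not lean one way throughout. All of this stands. It makes the point smaller, but it does not supply the missing counting rule or a comparison with equal opportunity.

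A reader might infer four stronger things that the documents do not support.
- *That this is the main tolerability comparison.* It is one of nine overview categories, and no safety comparison is designated main or confirmatory.
- *That the SAP excludes risankizumab events after Week 16.* This is an inference from the schedule. The SAP is silent, and SAP 9.0 counts risankizumab exposure to 84 days after the last injection.
- *That the protocol makes study discontinuation a safety category which the SAP dropped.* The words "only if they result in discontinuation from the study" in protocol 6.1.1.1 belong to the conditions under which laboratory abnormalities and vital-sign changes count as AEs. They define no analysis.
- *That the row runs about a third too low on risankizumab, for example 16.7% in place of 24%.* That figure is 1 − 0.76^(112/168). It applies a FUMADERM rate to risankizumab and assumes a constant hazard. Protocol 3.2 places gastrointestinal complaints on FUMADERM especially in the initial weeks, so a constant hazard is doubtful there too.

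**Conclusion.** The point holds as a gap in definition and an unequal comparison, not as a demonstrated bias. The row gives risankizumab 112 days of opportunity and FUMADERM 168, no planned analysis corrects it, and the SAP does not say how to count AE-driven withdrawal after the third injection. If such cases go uncounted, the direction favours risankizumab.

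The size is not known. Under a constant hazard and an assumed Week 16 rate of 1% to 5%, the shortfall is about 0.5 to 2.4 percentage points, or 0.3 to 1.3 of 55 subjects. That is unlikely to change the conclusion. The cut-off could matter if risankizumab stopping were about 9% or more, and nothing in the documents suggests such a rate. Mostly early stopping on FUMADERM would shrink the effect further. This is a cheap improvement to make before database lock.

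**What to change.** In SAP 11.2.1, keep the existing row and add one: *TEAE leading to discontinuation of study drug or premature discontinuation of the study, up to the Week 24 visit*. Present it for both arms in the Safety Population, with the same Fisher test and its own table by system organ class and preferred term. State that an AE-driven study withdrawal after the last risankizumab injection counts. The treatment-emergent windows can stay as they are.

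Optionally, show the drug-only row cut at Day 113 in both arms as supportive. It should not replace the full row, because it drops eight weeks of FUMADERM data.

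The cost is SAP wording plus one row and one table. Protocol 5.4.1 already requires the date of last dose and the primary reason for early termination to be recorded. The risankizumab count may come out slightly higher. Dosing and stopping rules are unchanged.

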**2. Adverse Events by System Organ Class and Preferred Term**

TEAEs will be summarized and presented using primary Medical Dictionary for Regulatory Activities (MedDRA) system organ classes (SOCs) and preferred terms (PTs). The SOCs will be presented in alphabetical order, and the PTs will be presented in alphabetical order within each SOC.

Subjects reporting more than one adverse event for a given MedDRA preferred term will be counted only once for that term (most severe incident for the severity tables and most related incident for the relationship tables). Subjects reporting more than one type of adverse event within a SOC will be counted only once for that SOC. Subjects reporting more than one type of adverse event will be counted only once in the overall total.

TEAEs will also be summarized presenting PTs in descending order of frequency in the risankizumab arm.

In addition, the number and percentage of adverse events with causal relationship as assessed by the investigator, between the events and the study drug will be summarized using the same conventions described above.

**3. Adverse Events by Maximum Severity**

The investigator will use the following definitions to rate the severity of each adverse event:

- Mild – The adverse event is transient and easily tolerated by the subject.
- Moderate – The adverse event causes the subject discomfort and interrupts the subject's usual activities.
- Severe – The adverse event causes considerable interference with the subject's usual activities and may be incapacitating or life-threatening.

Adverse events will be summarized by maximum severity. If a subject has an adverse event with unknown severity, then the subject will be counted in the severity category of "unknown," even if the subject has another occurrence of the same event with a severity present. The only exception is if the subject has another occurrence of the same adverse event with the most extreme severity. In this case, the subject will be counted under the "Severe" category.

#### **4. Adverse Events by Maximum Relationship**

Adverse events will be summarized by maximum relationship to study drug, as assessed by the investigator. Relationship of an AE to study drug is assessed by the investigator and collected in the CRF as 'Reasonable possibility' or 'No reasonable possibility.' If a subject has an adverse event with unknown relationship, the subject will be counted in the relationship category of "unknown," even if the subject has another occurrence of the same event with a relationship of "No reasonable possibility." If the subject has another occurrence of the same adverse event with a relationship assessment of "Reasonable possibility," the subject will be counted under the "Reasonable possibility" category.

A listing of all pretreatment (i.e., events start prior to the first study drug injection) serious adverse events will be provided.

The following tables are planned.

**Treatment-emergent adverse events will be summarized as follows:**

- Grouped by SOC and PT
- Grouped by SOC, PT and maximum relationship to study drug
- Grouped by SOC, PT and maximum severity
- By PT in descending order of frequency in the risankizumab arm.

**Treatment-emergent SAEs will be summarized as follows:**

- Grouped by SOC and PT

- By PT in descending order of frequency in the risankizumab arm.
- A by-subject listing will be provided

**Pre-treatment SAEs will be summarized as follows:**

- A by-subject listing will be provided

**Treatment-emergent adverse events leading to death or premature discontinuation of study drug will be summarized as follows:**

- Grouped by SOC and PT
- Separate listings by subject for deaths and premature terminations of study drug due to adverse events will be provided.

**Treatment-emergent areas of safety interest will be summarized as follows:**

- Grouped by SOC and PT
- A listing by subject will be provided.

**Areas of Safety Interest**

Areas of Safety Interest groupings are listed in [Table 6](#). These events are of interest due to a higher rate in the moderate to severe psoriasis population, or of interest for all immunoglobulin products or products in general.

**Table 6. Areas of Safety Interest**

ASI Grouping	Categories (ASI)	Search Criteria	Terms to Display	Include in AE Overview (Y/N)
Adjudicated CV Events	MACE	Adjudicated events	
Display underlined terms defined by the following adjudicated terms:
 
 
• CV Death which includes CETERM values: Fatal CV, Fatal PE, Fatal Non-Cardiac/Non-Neuro Arterial Thrombosis/Thromboembolism, Undetermined Death, Not assessable death (cardiac/neuro/thrombotic), Fatal Stroke
 
• Myocardial infarction
 
• Stroke
 
	Y
	Extended MACE	Adjudicated events	
Display underlined terms from MACE and underlined terms below:
 
 
• Hospitalization for Unstable Angina
 
• Coronary Revascularization Procedures
 
	N
Serious infections, TB, fungal and opportunistic infections (including herpes zoster)	Serious infections	SOC Infections and Infestations, serious events only	PTs	Y
	TB	Tuberculosis (including Investigations) CMQ (code 80000033)	PTs	Y
	Opportunistic infections	Opportunistic infections CMQ (code 80000073)	PTs	N

**Table 6. Areas of Safety Interest (Continued)**

ASI Grouping	Categories (ASI)	Search Criteria	Terms to Display	Include in AE Overview (Y/N)
Serious infections, TB, fungal and opportunistic infections (including herpes zoster) (Continued)	Fungal infections	Fungal infections CMQ (code 80000063)	PTs	N
	Herpes Zoster	Herpes zoster CMQ (code 80000175)	PTs	N
Malignancies	All possible malignancies	Narrow – Malignancies (SMQ 20000090)	PTs	N
	Malignant Tumours	Narrow – Malignant tumours (SMQ 20000194)	PTs	Y
	Non-melanoma skin cancer (NMSC)	Broad – Skin malignant tumours (SMQ 20000204) excluding terms identified by the Melanoma CMQ (code 80000119)	PTs	N
	Malignant Tumours excluding NMSC	'Malignant Tumours excluding NMSC' is identified by the 'Malignant Tumours' search excluding terms identified by the 'Non-melanoma skin cancer (NMSC) search.	PTs	Y

